## **Trial Summary**

Trial Title	Micro thin Descemet's stripping automated endothelial keratoplasty (Micro thin-DSAEK) versus Descemets membrane endothelial keratoplasty (DMEK): A randomized controlled clinical trial of corneal transplant outcomes and visual function	
Internal ref. no. (or short title)	Microthin DSAEK Vs DMEK	
Clinical Phase	Not applicable	
Trial Design	RCT	
Trial Participants	All patients referred to Addenbrooke's corneal service with endothelial dysfunction requiring corneal transplantation, and with no significant ocular comorbidities.	
Planned Sample Size	56 eyes of 56 patients randomised into two arms (28 eyes in each arm)	
Treatment	A Single Surgical intervention- corneal endothelial keratoplasty	

	(Microthin DSAEK or DMEK)			
Follow up duration	12 months			
Planned Trial Period	Aug 2016 – April 2020			
	Objectives	Outcome Measures		
Primary				
	Functional (Visual) Improvement	Improvement in LogMAR visual Acuity		
Secondary	
 
Post-operative evaluation of transplant function
 
Intraoperative and postoperative complications
 
Patient satisfaction
 
	
 
Transplant survival
 
Post-operative complications including:         
 
Transplant detachment
 
primary transplant failure
 
Transplant rejection
 
Loss of Endothelial cell density
 
 
 
Patient satisfaction questionnaire
 
		
Investigational Medicinal Product(s)	Microthin DSAEK surgery or DMEK surgery			
Formulation, Dose, Route of Administration	N/A			

## **Background and Literature review**

Corneal disorders resulting in corneal opacification is a significant cause of blindness in the UK and remains the second most common cause of blindness in the developing world. Recent innovations in corneal transplant techniques (Endothelial keratoplasty) have shown significant benefit to patients in relation to visual function, rapid post-operative recovery, minimal hospital stay and fewer complications. Endothelial transplants are prepared from human cadaveric donor corneas either using a mechanized microkeratome (Microthin DSAEK) or by manual dissection (DMEK) with variations in surgical technique. Both these techniques are currently available and practised at Addenbrooke's eye unit for patients requiring corneal endothelial keratoplasty. A brief description of these two procedures is provided below:

## Microthin DSAEK

In Microthin DSAEK the endothelial transplant is prepared from the cadaveric human donor cornea using a mechanised microkeratome with transplant thickness varying between 70-130 microns. The DSAEK endothelial transplant consists of a monolayer of endothelial cells on the descemets membrane with posterior stromal layer. The conventional DSAEK procedure in comparison yields transplant thickness averaging 170microns with a wide variance between 70-250microns with less than optimum visual results. By regulating the corneal donor thickness using a stromal dehydration technique we have shown a reliable way to create an endothelial transplant thickness of 100microns with minimal variance, termed microthin DSAEK. This technique will be compared to DMEK in this trial.

## DMEK

In this procedure the endothelial transplant is prepared by manual peeling of the descemets membrane, which consists of a monolayer of endothelial cells without the posterior corneal stroma measuring 15-20 microns in thickness.

Both transplants (MT-DSAEK and DMEK) are delivered to the eye using a sterile disposable surgical injecting instrument. And the attachment of the transplant to the host cornea is assisted with an air bubble in the anterior chamber.

There is evidence in the literature on the widespread use of both these techniques and several studies comparing **conventional** DSAEK with DMEK. However, there has not been an attempt in literature to compare **Microthin** DSAEK with DMEK. Also, these trials have been retrospective and not randomised. Our study proposes a randomised controlled comparison of outcomes between Microthin DSAEK and DMEK to identify the effect of variations in corneal transplant preparation techniques in the field of corneal endothelial keratoplasty to visual outcomes.

## **Objectives and Outcome measures**

In this proposal, we aim to undertake a randomized controlled clinical trial comparing Microthin DSAEK and DMEK to assess visual improvement, complications, corneal transplant survival up to 12 months and patient satisfaction.

## The Primary end point is:

1. The improvement in vision measured in LogMAR units at 12 months.

The time points will be pre-operative, at 6months and then at the last visit in 12months. Our hypothesis assumes to detect a 2 line difference in final visual outcomes between the groups.

## Secondary end points:

- 1. Graft thickness at 6months and at 12months and comparison between the two arms. Hypothesis will be a difference of at least 50microns thickness between the two types of graft.
- 2. Endothelial count at 6m and at 12m visit. Hypothesis is no difference in the two arms.

- 3. Transplant survival at 12months.
- 4. Patient's satisfaction assessed using the questionnaire at 3 time points Before transplant surgery, at 6months and at last visit in 12months.
- 5. Complications rate of intra operative and post operative complications

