## Statistics and data analysis:

Based on power calculation, we estimate a sample size of 56 would provide sufficient power to the study. Group sample sizes of 28 and 28 achieve atleast 80% power to reject the null hypothesis of equal means when the mean difference of intended primary outcome measure is 0.1 with a standard deviation of 0.1 and with a significance level (alpha) of 0.050 using a two-sided two-sample equal-variance t-test. Only one eye of each patient will be enrolled in the study. An interim data analysis and power calculation will be undertaken at 6 months.

Further statistical analysis will be carried out using parametric and non-parametric tests depending upon the distribution of the results and comparing secondary outcome measures between the two arms of the study. The transplant thickness and relative visual gain would also be assessed using Pearson correlation coefficient. Kaplan-Meier limit analysis would be used to determine the cumulative probability of the transplant survival in the two groups with multi-variate analysis on factors influencing transplant survival.

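### The endothelial-count hypothesis is one of no difference, but the comparative tests the protocol states can only reject it, never support it

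*Protocol*

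**What the plan says.** Protocol, Secondary end points, item 2: "Endothelial count at 6m and at 12m visit. Hypothesis is no difference in the two arms". Item 1, on graft thickness at the same visits: "Hypothesis will be a difference of at least 50microns thickness between the two types of graft".

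Protocol, Statistics and data analysis: further analysis is to use "parametric and non-parametric tests depending upon the distribution of the results and comparing secondary outcome measures between the two arms". No individual test is named for either endpoint. The one power statement concerns the primary visual-acuity outcome: "Group sample sizes of 28 and 28 achieve atleast 80% power to reject the null hypothesis of equal means", for the case where the "mean difference of intended primary outcome measure is 0.1 with a standard deviation of 0.1", at a "significance level (alpha) of 0.050 using a two-sided two-sample equal-variance t-test".

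The protocol contains no equivalence or non-inferiority margin, no confidence-interval rule, no SD for endothelial count and no test against a 50-micron null. The Trial Summary describes the endothelial outcome differently, listing "Loss of Endothelial cell density" among the post-operative complications.

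**The concern.** A comparative test takes equal arms as its null hypothesis. A small p-value counts against equality, whereas a large one shows only that the data did not exclude it. If equality is what the investigators hope to show, the stated analysis cannot show it.

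The wording suggests that it is what they hope to show. For the primary endpoint and for graft thickness, the protocol uses the word hypothesis for the difference expected. In the sample-size paragraph it writes null hypothesis when it means a null. Read the same way, item 2 is a claim to be supported.

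At stake is the reporting of an outcome that the Trial Summary places among the complications. An uninformative result from 56 eyes could be written up as agreeing with the stated hypothesis, although the data remained compatible with a sizeable difference in cell count.

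**Working it through.** **Inputs.** From the protocol: 28 eyes per arm; two-sided alpha of 0.05 and an equal-variance t-test (both stated for the primary outcome); primary difference 0.1 with SD 0.1; graft thickness 70-130 microns (section Microthin DSAEK) and 15-20 microns (section DMEK). Assumed: the same alpha and a t-test are used for endothelial count, and all 28 eyes per arm supply a count. No SD for count is given, so results are in SD units.

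**1. The protocol's own power figure.** Standardised difference 0.1/0.1 = 1.0; noncentrality 1.0 × √(28/2) = 3.74 on 54 degrees of freedom. Exact t power is 95.7% (normal approximation 96.3%), so at least 80% is true as a lower bound. It concerns rejecting equality on visual acuity and says nothing about showing equality of cell counts.

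**2. Precision for endothelial count.** The 95% CI half-width is t(0.975, 54) × √(2/28) = 2.005 × 0.2673 = 0.536 SD. For illustration only, assumed SDs of 300 to 600 cells/mm² would make this about 161 to 321 cells/mm².

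**3. How often a real difference is missed.** With noncentrality d × √(28/2) = 3.742d, the noncentral t distribution gives:

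| True difference (SD) | Noncentrality | P(non-significant) |
|---|---|---|
| 0 | 0 | 95% (by definition of alpha) |
| 0.25 | 0.94 | 85% |
| 0.5 | 1.87 | 55% |
| 0.75 | 2.81 | 21% |

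Power reaches 80% only at a true difference of 0.76 SD. Non-significance is almost as likely at 0.25 SD as at zero, so it barely separates the two.

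**4. What a proper equivalence analysis could show.** The rule is to claim equivalence only if the whole CI lies within ± the margin. Power was simulated with 1,000,000 draws, 28 per arm and a true difference of zero:

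| Margin (SD) | Using 90% CI | Using 95% CI |
|---|---|---|
| 0.5 | 17% | 2% |
| 0.75 | 74% | 58% |
| 0.8 | 81% | 67% |
| 0.9 | 91% | 82% |

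For 80% power at a 0.5 SD margin, the approximate size per arm is 2 × ((1.645 + 1.282)/0.5)², rounded up to 69, with a 90% CI, or 2 × ((1.960 + 1.282)/0.5)², rounded up to 85, with a 95% CI. No margin is stated, so these figures show a range and are not a required sample size.

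**5. Graft thickness.** The protocol's ranges imply a difference between 70 − 20 = 50 and 130 − 15 = 115 microns. For assumed SDs of 15 to 30 microns, a test against zero has 96% to over 99.9% power when the true difference is only 30 microns, so its significance would not establish 50. A one-sided 0.025 test against 50 has the same 96% to over 99.9% power if the true difference is 80, because the distance from the null is again 30. The existing sample size is enough to answer the stated question on those assumptions.

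**The case against.** - **The phrase may be only a formal null.** No sentence in the protocol says that p > 0.05 will be taken as equality. A reader might infer that the investigators plan to report it so, but the document does not support that as a statement of fact. What stands is narrower: the usage elsewhere in the protocol favours reading item 2 as a claim, and the only stated analysis cannot support that claim. If a null was meant, the sentence still needs rewording.
- **Margins and intervals for secondary endpoints usually sit in the SAP, which is not shown.** That is fair, and their absence alone would be no finding. The point is a mismatch between a hypothesis and an analysis that the protocol itself states. A margin in the SAP would supply the missing rule but leave the protocol sentence in need of correction.
- **Sizes in cells/mm² are assumption.** This is correct. Only the SD-unit figures follow from the stated sample size.
- **A reader might infer that cell loss will be measured from the recipient's specular reading at the referral visit.** The protocol lists that test but never proposes it as a baseline. Comparing counts at 6 and 12 months between randomised arms is valid without one.
- **Thickness hardly matters.** Given the protocol's own ranges this is largely right, so it is kept only as a side remark.
- **Endothelial count is one of five secondary endpoints and did not drive the sample size.** This is also right, and it limits the severity.

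**Conclusion.** The concern holds as a mismatch between the stated hypothesis and the stated analysis for a secondary endpoint. With 28 eyes per arm the 95% CI extends about 0.54 SD either side of the estimate, and true differences of 0.25, 0.5 and 0.75 SD would be non-significant 85%, 55% and 21% of the time. A non-significant p-value therefore cannot be reported as confirming equal endothelial counts. Even with a correct equivalence rule, 28 per arm gives 80% power only for margins of about 0.8 to 0.9 SD or wider.

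These figures rest on a t-test at two-sided 0.05 with complete data; eyes without a count would widen the interval. The finding does not affect the primary sample-size statement. It should be corrected, but it does not threaten the trial's main conclusion.

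**What to change.** In Secondary end points, item 2, replace the no-difference hypothesis with estimation: the between-arm difference in endothelial count at 6 and at 12 months, each with a 95% CI. State that 'no relevant difference' may be written only if that interval lies within a justified margin fixed before unblinding, and that the result is otherwise inconclusive. The protocol plans an interim analysis at 6 months; if it covers this endpoint, the margin should be fixed before then.

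Two smaller edits:

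- For graft thickness, judge the 50-micron hypothesis by whether the lower confidence limit exceeds 50, not by a test against zero.
- If the cell-loss outcome in the Trial Summary is to be reported, reconcile it with the counts in Secondary end points and say what loss is measured from. A donor count could serve only if one is available; the protocol mentions none, so that is an assumption.

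The cost is wording and agreement on a margin, with no added patients or visits. The downside is a less favourable statement when the interval is wide, which is likely at this sample size unless the margin is generous.

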## **STUDY PROTOCOL**

## 1St Referral clinic visit

# The following investigations and tests would be undertaken by the relevant staff of the clinical research team

Visual acuity testing performed by staff nurse /HCA

Specular Microscopy (SM) / Pentacam (Pc) / Auto-refraction (AR) / Intraocular Pressure (IOP) check / afferent pupil defect (APD) and Dilatation / Patient Quality of Life (QOL) questionnaire – **Corneal Nurse** 

Slit Lamp examination – Doctor

If suitable for enrolment, research team will be approached if doctor not part of the research study.

Study and procedure discussed – research team to include Consultant / Corneal fellow and corneal specialist nurse

Patient recruited following satisfactory consent to participate and patient listed for their anaesthetic choice LA/GA with information leaflets and 4 weeks cooling off period to make decision to participate in the trial.

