## > 4weeks post op-

- vision / IOP / specular / OCT corneal nurse
- slit lamp examination research team
- o removal of sutures
- o Patient QOL questionnaire

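### The protocol names patient satisfaction as a secondary endpoint but schedules only a quality-of-life questionnaire, and never says that the two are the same

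*Protocol*

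**What the plan says.** Three places in the Protocol name the construct as satisfaction. The Trial Summary gives it as the third secondary objective, with the outcome measure "Patient satisfaction questionnaire". The section Objectives and Outcome measures repeats it among the aims. The list under Secondary end points fixes the timing: "Patient's satisfaction assessed using the questionnaire at 3 time points Before transplant surgery, at 6months and at last visit in 12months".

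The visit schedule uses another name. The first referral clinic visit lists a "Patient Quality of Life (QOL) questionnaire", and the 4-week visit lists a "Patient QOL questionnaire". The same entry stands at the 6-month and 12-month visits. The closing section, which describes the tests used before and after surgery, covers the imaging, refraction, pressure and pupil tests but not the questionnaire.

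On analysis, the section Statistics and data analysis says only that secondary outcomes will be compared between the arms with parametric or non-parametric tests, chosen by how the data are distributed.

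**The concern.** Satisfaction and quality of life are different constructs. A site that follows the schedule will hand out a quality-of-life form, while a reader of the endpoint list will expect a satisfaction result. Because the protocol neither names the instrument nor equates the two terms, the label on the reported result would not be secured by what was collected.

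The pre-operative reading makes the meaning matter for the analysis. If the form is a quality-of-life scale, that reading is a baseline and should be used as one. If a rating of the operation were meant, there would be no baseline to use. The protocol does not say which applies. This is the trial's only patient-reported endpoint, so no other listed endpoint could fill the gap.

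**Working it through.** No sample-size arithmetic applies. The check sets the endpoint list beside the schedule and counts.

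**1. Names and time points, side by side.**

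| Time point | Secondary end points (satisfaction) | Visit schedule |
|---|---|---|
| Before surgery | listed | QOL form (first referral visit) |
| 1 week | not listed | no form |
| 4 weeks | not listed | QOL form |
| 10 weeks | not listed | no form |
| 6 months | listed | QOL form |
| 9 months | not listed | no form |
| 12 months | listed | QOL form |
| Total | 3 | 4 |

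The endpoint list's own count of three is reproduced: each of its three time points has a scheduled form. The difference is 4 − 3 = 1, the 4-week form. Of the four scheduled forms, none is called a satisfaction questionnaire.

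**2. Does the extra form conflict with the endpoint?** It does not. The endpoint is limited to three time points, and 4 weeks is not among them. The protocol collects more often than its endpoints need elsewhere too:
- Vision has three endpoint time points (pre-operative, 6 and 12 months) but is also taken at 1, 4 and 10 weeks and at 9 months.
- The endothelial count is an endpoint at 6 and 12 months, but specular microscopy is also done at 4 weeks, 10 weeks and 9 months.

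**3. Can the pre-operative score serve as a covariate?** It can. The form is completed at the first referral visit, and allocation takes place on the day of surgery, so the score precedes randomisation. The natural model is

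12-month score = a + b × arm + c × pre-operative score + error,

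with b as the treatment comparison. Relative to a plain comparison of 12-month scores, the residual variance is multiplied by about 1 − ρ², where ρ is the correlation between the pre-operative and 12-month scores. The protocol gives no value for ρ, so the gain cannot be stated as a number. Apart from the small cost of estimating one more coefficient, adjustment does not lose precision.

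**4. Effect on the sample size.** There is none. The calculation concerns the primary outcome: "Group sample sizes of 28 and 28 achieve atleast 80% power to reject the null hypothesis of equal means". With difference 0.1 and standard deviation 0.1, the standardised difference is 0.1 / 0.1 = 1, and 28 per arm gives 95.7% power by the two-sided t-test, which meets the stated minimum. Nothing in that calculation uses the questionnaire.

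**The case against.** The strongest reply is that this is a slip of terminology. The three endpoint time points coincide with three of the four scheduled forms, and a pre-operative reading fits a quality-of-life scale. One questionnaire under two names is therefore the likeliest explanation. The form's items are not shown and may include satisfaction with vision. The choice of analysis time point and the use of a baseline are often left to a statistical analysis plan, which is not at hand.

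Much of this stands, and it rules out three stronger readings that a reader might infer:

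- *That the trial would report quality of life as satisfaction with the surgical technique.* The protocol speaks only of patient satisfaction, not of satisfaction with a technique or an operation, and the content of the form is unknown. Mislabelling is a risk here and not an established outcome.
- *That a pre-operative satisfaction score is meaningless.* That follows only if satisfaction with the transplant is meant, which the protocol does not say. A pre-operative reading is an ordinary baseline for quality of life or for satisfaction with vision.
- *That three time points against four is a contradiction, leaving the 4-week score open to use after the data are seen.* The endpoint list already excludes 4 weeks.

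The reply does not remove the mismatch in names. Both terms stand in the protocol itself, and a later analysis plan would still have to choose between them.

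**Conclusion.** The point holds as a mismatch between a named endpoint and the only questionnaire scheduled for it. As written, a satisfaction conclusion could rest on a quality-of-life score. One of five listed secondary endpoints is affected. No endpoint reading is missing, and the primary endpoint, sample size and power are untouched. Severity is minor.

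The conclusion rests on the protocol alone. It assumes that no other questionnaire is given outside the visit schedule and that the text at hand does not omit a statement equating the two terms. If the form proves to contain a defined satisfaction score, the endpoint's name can stay, and what remains is to say so. The baseline-adjusted comparison is an improvement on the plain two-arm tests now described; it does not correct an error in them.

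**What to change.** Reconcile the Trial Summary, Objectives and Outcome measures, and Secondary end points with the visit schedule:

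1. Name the instrument and its score, and use one term for it throughout. If it is a quality-of-life scale, call the endpoint a QOL score.
2. Compare 12-month scores between arms, adjusted for the pre-operative score, in place of an unadjusted two-arm test. Treat 6 months as supporting.
3. Keep the three endpoint time points and label the 4-week reading exploratory.

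The cost is a protocol wording change and a slightly different secondary analysis. It needs no new visit, form or patient.

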## **Trial Procedures**

**Recruitment**: - All patients referred to the corneal service in Addenbrookes hospital with endothelial disease and no significant ocular comorbidities requiring endothelial keratoplasty will be invited to participate in the trial.

## **Inclusion Criteria:**

- All patients between 50-90 years of age attending/ referred to Addenbrooke's Hospital (Cambridge University Hospitals NHS Trust) corneal tertiary referral service for management of corneal diseases affecting the endothelial function and requiring endothelial lamellar keratoplasty.
- 2. Patients with visual acuity between 6/9 to Perception of Light will be included in the study.

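### Eligibility down to perception of light does not fit a LogMAR change score sized with an SD of 0.1: one off-chart eye can distort the estimate and remove the power

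*Protocol*

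**What the plan says.** Three parts of the protocol bear on this point.

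- **Inclusion Criteria:** "Patients with visual acuity between 6/9 to Perception of Light will be included in the study". The Exclusion criteria set no further acuity limit.
- **The Primary end point is:** "The improvement in vision measured in LogMAR units at 12 months", with a pre-operative time point. The Trial Summary also names improvement as the primary outcome. The same endpoint section then words the hypothesis differently: "Our hypothesis assumes to detect a 2 line difference in final visual outcomes between the groups".
- **Statistics and data analysis:** "Group sample sizes of 28 and 28 achieve atleast 80% power to reject the null hypothesis of equal means", for a "mean difference of intended primary outcome measure is 0.1 with a standard deviation of 0.1", at a "significance level (alpha) of 0.050 using a two-sided two-sample equal-variance t-test". Other methods appear only for further analysis, which "will be carried out using parametric and non-parametric tests depending upon the distribution of the results".

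The protocol gives no LogMAR value for perception of light or for any other acuity that cannot be read on a chart.

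**The concern.** The eligibility range and the endpoint are on different scales. Counting fingers, hand movements and perception of light are categories, not letter-chart readings. For an eye in one of these categories the 12-month acuity can be a measurement, but the baseline is a number that someone chooses, and the improvement inherits it. Any reasonable choice is far from the rest of the sample.

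A mean change compared by t-test is sensitive to such a value. With 28 eyes per arm, a single one moves the arm mean noticeably and raises the variance well above what the sample size allows for. At stake are the size of the estimated difference and the trial's ability to detect it.

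**Working it through.** **1. The plan's own figure.** Inputs from Statistics and data analysis: difference 0.1, SD 0.1, 28 per arm, two-sided alpha 0.05, equal-variance t-test. The exact power is 95.7%, so the claim of at least 80% is true as a lower bound. (80% needs only 17 per arm.) With 28 per arm and a difference of 0.1, power is 86.5% at SD 0.12, 80.7% at SD 0.13 and 77.7% at SD 0.135. The design therefore tolerates an SD of about 0.13 before it drops below 80%.

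**2. Assumptions.** The documents give none of these, so ranges are used:
- LogMAR value substituted for an off-chart baseline: 2.0 to 3.0
- that eye's 12-month acuity: 0.1 to 0.2
- improvement of a typical eye: 0.2 to 0.6

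For scale, the best eligible baseline, 6/9, is log10(9/6) = 0.18.

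**3. Shift in the arm mean from one such eye.**
Excess = substitute − final acuity − typical improvement. Shift = excess / 28.
- Smallest: (2.0 − 0.2 − 0.6)/28 = 1.2/28 = 0.043
- Middle case: (2.7 − 0.2 − 0.4)/28 = 2.1/28 = 0.075
- Largest: (3.0 − 0.1 − 0.2)/28 = 2.7/28 = 0.096

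Against the 0.1 of the power calculation this is 43% to 96%. Against 2 lines (0.2, at the usual 0.1 per line) it is 21% to 48%. To exceed half of 0.1 the excess must be above 0.05 × 28 = 1.4. To exceed half of 0.2 it must be above 0.1 × 28 = 2.8, which is outside the range.

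**4. How much is due to the choice of substitute.**
- 2.3 or 2.7: 0.4/28 = 0.014
- 2.3 or 3.0: 0.7/28 = 0.025
- 2.0 or 3.0: 1.0/28 = 0.036

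Most of the shift in step 3 therefore comes from having an extreme baseline in one arm, and a smaller part from which value is substituted.

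**5. Effect on the SD.** Let the other eyes have the planned SD of 0.1, and take the middle case (excess 2.1).
- Variance in the arm with the eye: (26 × 0.01 + 2.1² × 27/28)/27 = 0.167, so SD 0.41
- Pooled SD: √((0.167 + 0.01)/2) = 0.30

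Across the full range of assumptions the pooled SD is 0.19 to 0.37, always above the 0.13 from step 1.

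**6. Effect on power.** Simulated trials with a true difference of 0.1 and one off-chart eye (40,000 for the t-test, 4,000 for the rank test):

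| Excess | Arm with the eye | Mean estimated difference | t-test power | Rank-test power |
|---|---|---|---|---|
| none | – | 0.100 | 96% | 95% |
| 1.4 | worse | 0.050 | 1% | 90% |
| 1.4 | better | 0.150 | 91% | 96% |
| 2.1 | worse | 0.025 | 0% | 90% |
| 2.1 | better | 0.175 | 71% | 97% |
| 2.4 | worse | 0.015 | 0% | 90% |
| 2.4 | better | 0.186 | 58% | 96% |

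The t-test loses power whichever arm receives the eye, because the variance rises in both cases.

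**7. Can one eye produce a false positive?** With no true difference and the middle case, the expected difference is 0.075. Its standard error is 0.30 × √(2/28) = 0.08, so t is about 0.9, far from significance.

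**The case against.** The strongest objections, and what stands of each:

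- **A conversion rule may be in the SAP, which is not shown.** This stands, and its absence from the protocol is not the point. A rule would supply a number, but it would not turn the category into a measurement or make an SD of 0.1 fit a change score with such a baseline.
- **The hypothesis speaks of final visual outcomes.** On that reading the baseline does not enter the outcome and most of the problem goes away. However, the named endpoint, in both the Trial Summary and the endpoint section, is improvement. The two wordings need to be reconciled, and the fix below does so.
- **The planned difference may be 2 lines, not 0.1.** The protocol states both. Against 2 lines one eye never accounts for half the difference under the assumed range, so both yardsticks are reported.
- **There may be no such eyes.** This stands. The protocol gives no expected number.
- **A rank test would cope.** It would, as step 6 shows, but the power calculation names the t-test and non-parametric methods are mentioned only for further analysis.

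A reader might infer that the primary endpoint cannot be measured in these eyes. That goes too far: only the baseline lacks a chart value. A reader might also infer that the arbitrary substitute alone could shift the result by most of the planned difference. Step 4 does not support this for substitutes of 2.0 to 3.0. Nor is it supported that one eye could create a significant result from nothing (step 7).

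**Conclusion.** The mismatch is real. The protocol admits eyes with no chart-measured baseline, makes LogMAR improvement its primary endpoint, and sizes the comparison of means with an SD that a single such eye would exceed. In the middle case one eye moves its arm's mean change by 0.075 and triples the pooled SD. Power for a true difference of 0.1 then falls from about 96% to about 0% or 71%, depending on the arm. The consequence is a distorted estimate and lost power rather than a false claim of benefit.

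These sizes rest on the assumed substitute, final acuity and typical improvement, on an SD of 0.1 in all other eyes, and on a change-score t-test. They apply only if at least one off-chart eye is enrolled.

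**What to change.** Make LogMAR acuity at 12 months the primary outcome, which agrees with the hypothesis as worded in the endpoint section. Compare the arms with adjustment for baseline LogMAR plus a yes/no indicator for an off-chart baseline. Give every off-chart baseline the same value, fixed in advance, so that the indicator absorbs the arbitrary choice. Add a rank-based sensitivity analysis. An eye still off-chart at 12 months would also need a pre-set value, and the rank-based analysis shows whether that value matters.

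This uses data already collected and excludes no one. It costs one or two degrees of freedom, and an off-chart eye that is alone in its category adds little information to the comparison. Restricting entry to eyes that can read the chart is an option for the sponsor, at the price of a narrower population. It is not a required change.
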